**C-reactive Protein:** Inflammation has been hypothesized to increase the risk of cancer although data from epidemiologic study are sparse. Many inflammatory conditions are well-known cancer precursors (Barrett's esophagus, chronic gastritis, hepatitis, pancreatitis, and ulcerative colitis). So, early correction of inflammatory conditions by chemoprevention may be theoretically very useful. C-reactive protein (CRP), a member of the pentraxin family of proteins involved with pattern recognition in innate immunity, is the principal downstream mediator of the acute-phase response and is primarily derived via the interleukin 6-dependent hepatic biosynthesis. Moreover, ultrasensitive CRP (hs-CRP) is an known index of subclinical systemic inflammation associated with increased risk for cardiovascular events and diabetes. Elevated levels of hs-CRP have been linked to colon cancer development and a recent meta-analysis including 1,918 lung cancer cases points to its implication also with lung cancer risk.

Given our previous experience in measuring hs-CRP in subjects at higher risk for breast cancer, we are interested in investigating change in hs-CRP also in subjects at higher risk of lung cancer.

**Cotinine:** Measurement of cotinine, the nicotine metabolite, provides an accurate estimate of recent tobacco smoke exposure and are able to account for individual differences in smoking practices, such as depth of inhalation and how much each cigarette is smoked.

**Prostaglandin (PGEM):** Prostaglandin synthesis is driven by the two COX. Prostaglandin E2 is the most abundant prostanoid in the human body and it has been implicated in various tumorigenic processes and

induces proliferation by activating at least two signalling pathways: Ras–Erk and glycogen synthase kinase-3 $\beta$  (GSK3 $\beta$ )– $\beta$ -catenin in colon and lung cancer cells. Circulating prostaglandin E2 is rapidly cleared by a single passage through the lungs and measurement of the metabolites is necessary to provide a reliable estimate for its actual production.

**Leukotriene E4 (LTE4):** Leukotriene E4 is an urinary metabolite indicating activation of the lipoxygenase pathway. To perform urine analysis for LTE4, we will show relationship between acetyl-salicylic acid (ASA) and the LTE4 shunt in healthy smokers.

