### 5.5 Concomitant Medications

Other NSAIDs or glucocorticosteroids should be avoided or limited. Any use of systemic or topic NSAIDs or glucocorticosteroids should be clearly documented (time, doses, routes, indications) and followed regularly.

If a participant requires pain relievers or antipyretics, the use of non-NSAIDs, e.g., acetaminophen, should be encouraged. It is not necessary to break the blind in most situations. A protonic pump inhibitor (PPI, omeprazole 20 mg/day tablet) will be added during the period of any NSAIDs or glucocorticosteroids treatment and will be stopped once NSAIDs or glucocorticosteroids are withdrawn.

Short courses of systemic NSAIDs or glucocorticosteroids (defined as up to 2 weeks at a time) are allowed. No more than 1 month total of off-protocol NSAIDs or glucocorticosteroids is allowed in a 6 months period. If it is anticipated that continuous NSAIDs or glucocorticosteroids will be needed or if more than 1 month of NSAIDs or glucocorticosteroids occurs during a 6 months period, the participant will stop study drug. However, since the participant will still undergo his/her yearly scan, they can still be assessed in an intent-to-treat analysis and thus do not come off the study. Non systemic glucocorticosteroids use is allowed without time restrictions.

All medications (prescription and over-the-counter), vitamin and mineral supplements, and/or herbs taken by the participant will be documented on the concomitant medication CRF and will include: 1) start and stop date, dose and route of administration, and indication. Medications taken for a procedure (e.g., biopsy) should also be included.

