## 10.2 Collection and Handling Procedures

All blood and urine samples will be withdrawn under fasting condition (at least 6 hours) preferably between 8 a.m. and 10 a.m. at each time point. Instructions about specimen handling and storage will be provided in a dedicated Manual of Procedures.

A total of **8 ml** of blood will be withdrawn for safety labs (at baseline, 6 and 12 months)

A total of **4.5 ml** of blood will be collected for **miRNA** (at baseline and 12 months) with the following recommendation for each blood withdrawal:

- 1) Patients should be fasting at least 6 hours before blood collection
- 2) Information about oral therapy with anti-inflammatory, anticoagulants, steroids or other drugs will be collected the same day.
- 3) Patients must have been free of any infection (including flu) and inflammatory diseases for a week prior to the collection of blood samples.
- 4) Before any instrumental or physical examination has been performed

Fasting (at least 6 hours) blood samples will be collected in all participants free of any infection (including flu) and inflammatory diseases for a week prior to the collection of blood samples at baseline and after 12 months of treatment. In order to avoid skin contamination, the first 3 mL of blood should not be used for serum preparation. Blood samples (4.5 ml) will be collected in tubes without anti-coagulant (white cap), left at room temperature for 30-60 minutes to clot, then spun at 3000 rpm (1000 g, Megafuge 2.0 – Heraeus) for 10 minutes at room temperature. The serum will be immediately removed slowly by using a plastic transfer pipette, leaving 0.5 cm remaining to avoid disturbing the serum-clot interface, dispensed in 0.6 ml aliquots (for a total of 4 aliquots) into 1.5 ml cryotubes (Thermo Fisher Scientific), specifically labeled with a barcode, and snap frozen in dry ice. Aliquots will then be transferred in a dedicated -80°C freezer.

A total of **7.5 ml** of blood will be collected into tubes containing clot activator for **hs-CRP** (at baseline, 6 and 12 months):

Morning fasting blood samples are centrifuged at 1850xg and one ml serum aliquots will be stored into 1.5 ml cryotubes (Thermo Fisher Scientific), specifically labeled with a barcode and transferred in a dedicated -80°C freezer.

A total of **7.5 ml** of blood will be collected into tubes containing clot activator for **TXB2** (at baseline, 6 and 12 months):

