Morning fasting blood samples will be collected and the time of blood draw will be reported. Samples will be incubated at 25°-37°C (77-98.6°F) for 1 hour and then centrifuged at 1000xg for 7 minutes. One ml serum aliquots will be stored into 1.5 ml cryotubes (Thermo Fisher Scientific), specifically labeled with a barcode and transferred in a dedicated -80°C freezer.

First morning **urine** samples (**15 ml**) should be collected under fasting conditions following the standard procedure for appropriate urine collection (may be provided) and samples should be kept refrigerated until arrival to hospital. Alternatively, samples should be collected under fasting conditions (15 ml) at the hospital in concomitance with blood draw. Urinary creatine will be determined on fresh specimen to normalize subsequent urinary biomarker results. The remaining sample will be aliquoted into 2.0 ml cryotubes, specifically labeled with a barcode and transferred in a dedicated -80°C freezer.

A total **2.5 ml** whole blood will be collected at baseline and 12 months of treatment in tubes containing

anti-coagulant CBC - Na-EDTA (red cap) and stored at -80°C in order to collect DNA and RNA for future unspecified analysis.

DNA will be purified using the QIAamp DNA Blood Mini Kit (QIAGEN) that is designed for processing up to 200 µl fresh or frozen human whole blood with an expected yield of 4-12ug of DNA, which is sufficient for all downstream sequencing and PCR analyses. RNA will be purified using the QIAamp RNA Blood Mini Kit (QIAGEN) specifically designed for extracting high-quality RNA (1-5ug yeald) for all low- and high-throughput screening technologies (qRT-PCR, microarray, RNA-seq).

All DNA/RNA samples will be stored at -80°C in the IEO biobank (IBBRI).

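### Month-6 hs-CRP falls outside the one-week infection-free rule, and permitted NSAID or steroid courses are not tied to biomarker sampling dates

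*Combined protocol and SAP*

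**What the plan says.** Section 10.2 opens the miRNA collection rules with the 4.5 ml draw, "at baseline and 12 months) with the following recommendation for each blood withdrawal". Item 3 of that list is the infection condition: "Patients must have been free of any infection (including flu) and inflammatory diseases for a week prior to the collection of blood samples". The paragraph that follows restates it "for a week prior to the collection of blood samples at baseline and after 12 months of treatment". Item 2 of the same list asks for drug use, including anti-inflammatories and steroids, to be recorded that day.

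hs-CRP is a separate 7.5 ml draw: "of blood will be collected into tubes containing clot activator for hs-CRP (at baseline, 6 and 12 months". Its own instruction is "Morning fasting blood samples are centrifuged at 1850xg and one ml serum aliquots will be stored into 1.5 ml cryotubes". For TXB2 the text is "Morning fasting blood samples will be collected and the time of blood draw will be reported". Section 7.3 asks only for fasting at month 6. A footnote to the Schedule of Events says that miRNA, PGEM and LTE4 are collected at baseline and month 12 only.

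The biomarker rationale in section 2.3 says that CRP "is the principal downstream mediator of the acute-phase response". Section 5.5 states: "Short courses of systemic NSAIDs or glucocorticosteroids (defined as up to 2 weeks at a time) are allowed". It caps the total at one month in any six and requires every course to be documented. Section 13.5 puts all three visits (baseline, 6 and 12 months) into the mixed model for secondary endpoints.

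**The concern.** The plan bars recent infection for miRNA but not for the marker that it describes as acute-phase. At baseline and month 12 the hs-CRP tube is scheduled at the same visit as the miRNA tube, so the rule protects it in practice. At month 6 nothing does. Samples taken during an infection would add variance to the month-6 hs-CRP comparison.

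The second gap concerns drugs. Section 2.2 says that NSAIDs act by inhibiting prostaglandins through COX-1 and COX-2, and PGEM measures prostaglandin E metabolites. A placebo participant sampled on an NSAID would tend to look treated on PGEM, and possibly on TXB2. Unlike infection noise, this has a direction: it shrinks the difference between arms. At entry, exclusion 4.2.1 covers only chronic NSAID use, so a baseline sample taken during a short course is also possible.

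**Working it through.** The plan states no figure for this point, so there is none to reproduce. The first step is to set the sampling rules side by side.

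| Sample | Visits (months) | Condition stated for sampling |
|---|---|---|
| miRNA blood (10.2) | 0, 12 | fasting; infection-free for one week; drugs recorded the same day |
| hs-CRP blood (10.2) | 0, 6, 12 | morning, fasting |
| TXB2 blood (10.2) | 0, 6, 12 | morning, fasting, time recorded |
| Urine for PGEM (10.2, Schedule of Events) | 0, 12 | fasting |

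Month 6 has an hs-CRP draw and no miRNA draw, so the infection condition does not reach it. No section defers a draw, sets a drug-free interval or flags a sample because of an NSAID or steroid course. Section 13.5 names no covariate for either.

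**Infection: illustrative size.** The infected share p, the fold rise F and the variance V of the log change are all assumptions. So is the log scale, because section 13.5 specifies only an identity link for normal data.

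- Added log variance = p(1 − p) × (ln F)². Inflation = 1 + added/V. Loss of effective sample = 1 − 1/inflation.
- Middle case (p = 0.05, F = 10, V = 1.0): 0.0475 × 5.30 = 0.25. Inflation is 1.25 and the loss is 20%.
- Low case (p = 0.03, F = 5, V = 1.0): 0.0291 × 2.59 = 0.075. Inflation is 1.08 and the loss is 7%.
- High case (p = 0.10, F = 10, V = 0.5): 0.09 × 5.30 = 0.48, and 0.48/0.5 = 0.95. Inflation is 1.95 and the loss is 49%. This takes the worst value of all three inputs.
- One infected participant among 64 in an arm (F = 10, V = 1.0): added variance = (1/64)(63/64) × 5.30 = 0.08, or 8%. The arm mean moves by ln(10)/64 = 0.04 log units.

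These figures concern month 6 alone. The model uses three visits, so the loss for the overall hs-CRP comparison would be smaller.

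**NSAID use: illustrative size.** Suppose a share f of placebo samples is taken on an NSAID that fully mimics aspirin on the marker, and samples in the aspirin arm do not change. The effect becomes (1 − f) times its true size. The documents give no biomarker effect, so I use 0.5 SD with 64 per arm, the values in the primary sample size (section 13.3), where a two-sided t-test has 80.1% power.

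- f = 0.05: 0.5 × 0.95 = 0.475 SD, power 76%.
- f = 0.10: 0.5 × 0.90 = 0.450 SD, power 71%.
- f = 30/182.5 = 0.164: 0.5 × 0.836 = 0.418 SD, power 65%. This is a ceiling, because it needs every placebo participant to use the full cap in section 5.5.

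**The case against.** The strongest reply is that the gap is small and partly managed already. Much of it stands.

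- The infection gap is one secondary marker at one intermediate visit. Exclusion 4.2.5 also bars active infection at entry, and the month-12 hs-CRP is protected by the shared visit.
- A reader might infer that a single infected sample could overwhelm the aspirin effect. The arithmetic does not support that: one 10-fold value among 64 moves the arm mean by about 0.04 log units.
- A reader might also infer bias from infection. In randomised, blinded arms it should occur about equally, so the cost is precision.
- Section 5.5 says that other NSAIDs and steroids should be avoided or limited, encourages acetaminophen, and requires dates, dose, route and indication. Section 7.1 records medications and adverse events at month 6. The data needed to flag samples therefore exist, and what is missing is a rule for using them.
- A reader might infer that the compliant population is compromised. It is not. Section 5.7 makes TXB2 an additional measure beside self-report, calendar and dose count, and sections 13.4 and 13.6 define compliance as at least 80% of drug taken.

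One reply does not carry. The list heading refers to each blood withdrawal, which might be read as every blood sample in the study. It sits under the miRNA draw, however, and the restatement names only baseline and month 12. A further limit is that the Manual of Procedures was not available. It is described as covering handling and storage, but it might add a sampling rule.

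**Conclusion.** The point holds as a cheap improvement to secondary biomarker data. On the text, month-6 hs-CRP may be drawn during an infection, and permitted NSAID or steroid courses are not kept away from biomarker sampling. The first adds noise that should be balanced between arms. The second could narrow the contrast on PGEM at baseline and month 12, and possibly on TXB2 at all three visits; the documents do not say how other NSAIDs affect TXB2. The CT primary endpoint and its sample size are unaffected.

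Any size is an assumption and not a document figure. The middle case is about 25% more variance in month-6 log hs-CRP change, within a range of 8% to 95% that is driven entirely by the assumed infection rate, fold rise and variance.

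**What to change.** In section 10.2 and the Manual of Procedures, apply the one-week infection-free condition to the hs-CRP draw at all three visits, including month 6. If it is not met, or if a short NSAID or systemic steroid course is ongoing, defer the biomarker draws within the existing ±2 week window. That window applies to months 6 and 12. At baseline, any deferral has to fit the section 7.1 limit from CT to randomization (61 days, or 42 days for those who qualify on the three-month scan).

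Where deferral is not possible, take the sample and flag it from the same-day medication and adverse-event records (at baseline, from medications and baseline symptoms). Keep flagged samples in the main analysis and add to section 13.5 a prespecified sensitivity analysis without them. State there that this exclusion conditions on post-randomisation events: if the need for analgesics differs by arm, it can introduce bias of its own.

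The cost is a few sentences and a few draws moved within the window. Some samples will still be flagged, because a two-week course, or an illness plus one clear week, may not fit. Treatment, permitted medication, visits and sample size do not change.

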### **10.3 Shipping Instructions**

Samples will be collected and stored locally till shipping to EIO after study completion. Instructions about specimen handling and storage will be provided in a dedicated Manual of Procedures.

All samples will be shipped in compliance with the International Air Transport Association (IATA) Dangerous Goods Regulations.

### **10.4 Tissue Banking**

Aliquots will be transferred in a dedicated -80°C freezer at the IBBRI and kept till measurement.

Biologic specimens collected during the conduct of each clinical trial that are not used during the course of the study will be considered deliverables under the contract and thus the property of the NCI. At study completion, NCI reserves the option to either retain or relinquish ownership of the unused biologic specimens. If NCI retains ownership of specimens, the Contractor shall collect, verify and transfer the requested biologic specimens from the site to a NCI-specified repository or laboratory at NCI's expense.

## **11. REPORTING ADVERSE EVENTS/ADVERSE DRUG REACTIONS**

**DEFINITION ADVERSE EVENT (AE):** AE means any untoward medical occurrence associated with the use of a drug in humans, whether or not considered drug related. An AE can therefore be any unfavorable and unintended sign, symptom, or disease temporally associated with participation in a study, whether or not related to that participation. This includes all deaths that occur while a participant is on a study.

Please note that all abnormal clinical laboratory values that are determined to be of clinical significance based on a physician's assessment are to be reported as AEs. Those labs determined to be of no clinical significance or of unknown clinical significance (per the physician's assessment) should not be reported as AEs. Any lab value of unknown clinical significance should continue to be investigated/followed-up further for a final determination, if possible.

A list of AEs that have occurred or might occur (Reported Adverse Events and Potential Risks) can be found in §6.2, Pharmaceutical Information, as well as the Investigator Brochure or package insert.

**DEFINITION ADVERSE DRUG REACTION (ADR):** all untoward and unintended responses to an investigational medical product related to any dose administered (Directive 2011/20/EC).

Comment: all AEs judged by either the reporting investigator or the sponsor as having a reasonable causal relationship to a medical product qualify as ADR. The expression of reasonable causal relationship means

to convey in general that there is evidence or argument to suggest a causal relationship (ENTR/CT/ 3 April 2006).

Unexpected ADR: an ADR, the nature and severity of which is not consistent with the applicable product information (Directive 2001/20/EC-art. 2 §p; art 16§1)

## 11.1 Adverse Events

### 11.1.1 Reportable AEs/ADRs

All AEs that occur after the informed consent is signed and baseline assessments are completed (including run-in) must be recorded on the AE CRC (paper and/or electronic) whether or not related to study agent.

### 11.1.2 AE Data Elements:

The following data elements are required for adverse event reporting.

- AE verbatim term
- System Organ Class (SOC)
- Common Terminology Criteria for Adverse Events v4.0 (CTCAE) AE term
- Event onset date and event ended date
- Severity grade
- Attribution to study agent (relatedness)
- Whether or not the event was reported as a serious adverse event (SAE)
- Whether or not the subject dropped due to the event
- Outcome of the event

### 11.1.3 Severity of AEs/ADRs

11.1.3.1 Identify the AE using the NCI Common Terminology Criteria for Adverse Events (CTCAE) version 4.0. The CTCAE provides descriptive terminology and a grading scale for each adverse event listed. A copy of the CTCAE can be found at [http://ctep.cancer.gov/protocolDevelopment/electronic\\_applications/ctc.htm](http://ctep.cancer.gov/protocolDevelopment/electronic_applications/ctc.htm)

AEs will be assessed according to the CTCAE grade associated with the AE term. AEs that do not have a corresponding CTCAE term will be assessed according to the general guidelines for grading used in the CTCAE v4.0. as stated below.

#### CTCAE v4.0 general severity guidelines:

Grade	Severity	Description
1	Mild	Mild; asymptomatic or mild symptoms; clinical or diagnostic observations only; intervention not indicated.
2	Moderate	Moderate; minimal, local or noninvasive intervention indicated; limiting age-appropriate instrumental activities of daily living (ADL)*.
3	Severe	Severe or medically significant but not immediately life-threatening; hospitalization or prolongation of hospitalization indicated; disabling; limiting self-care ADL**.
4	Life-threatening	Life-threatening consequences; urgent intervention indicated.

5	Fatal	Death related to AE.
---	-------	----------------------

## ADL

\*Instrumental ADL refers to preparing meals, shopping for groceries or clothes, using the telephone, managing money, *etc.*

\*\*Self-care ADL refers to bathing, dressing and undressing, feeding self, using the toilet, taking medications, and not bedridden.

### 11.1.4 Assessment of relationship of AE/ADR to treatment

The possibility that the adverse event is related to study agent will be classified as one of the following: not related, unlikely, possible, probable, definite.

### 11.1.5 Follow-up of AEs/ADRs

All AEs, including lab abnormalities that in the opinion of the investigator are clinically significant, will be followed according to good medical practices and documented as such.

## 11.2 Serious Adverse Events

11.2.1 DEFINITION: According the European Directive 2001/20/EC and Fed. Reg. 75, Sept. 29, 2010 defines SAEs as those events, occurring at any dose, which meet any of the following criteria:

- Results in death
- Is life threatening (*Note: the term life-threatening refers to an event in which the patient was at risk of death at the time of the event; it does not refer to an event which hypothetically might have caused death if it were more severe.*)
- Requires inpatient hospitalization or prolongation of existing hospitalization
- Results in persistent or significant incapacity or substantial disruption of the ability to conduct normal life functions
- Is a congenital abnormality/birth defect
- Important medical events that may not result in death, be life-threatening or require hospitalization may be considered serious when, based upon appropriate medical judgment, they may jeopardize the patient or subject and may require medical or surgical intervention to prevent one of the outcomes listed.

### 11.2.2 Reporting Serious Adverse Events

The Sponsor is responsible for AE/ADR reporting to Regulatory Authority and Ethic Committee according to local regulation.

The Principal Investigator will notify the Sponsor of any SAE within 24 hours of knowledge of the event. All SAEs (irrespective of suspected causation) which occur while the patient is on study must be reported by the investigator to the local ethics committee regulatory office and to Servizio Farmacia - European Institute of Oncology ([contact])

All relevant information about serious, unexpected adverse events suspected to be related to the investigational product that are fatal or life-threatening must be reported by the Sponsor to the Health Authority as soon as possible and in any case no later than seven days after knowledge of such a case. Relevant follow-up information for these cases will be subsequently submitted within an additional eight days. All other serious unexpected events suspected to be related to the investigational product must be reported as soon as possible, but within a maximum of 15 days of first knowledge by investigator.

The organization that experiences the serious adverse event (SAE) should report the SAE to the following 3 entities: 1) NCI DCP, 2) DCP's regulatory contractor CCSA, and 3) MDACC, the CLO. Detailed reporting instructions are provided below.

11.2.2.1 The Lead Organization and all Participating Organizations will report SAEs on the DCP SAE form found at [http://prevention.cancer.gov/sites/default/files/uploads/clinical\\_trial/SAE-form.pdf](http://prevention.cancer.gov/sites/default/files/uploads/clinical_trial/SAE-form.pdf).

